**Figure 1 Overall Study Design and Dose-escalation**

Dotted lines indicate optional cohorts. See [Table 1](#) for additional information.

Escalation to the next single dose cohort will be based primarily on the safety and available PK data through 24 hours post-single dose in the previous cohorts. The MAD phase may start after a wash-out period of approximately 1-week, providing that the safety information through 24 hours post-dose in the SAD phase at the same cohort, and available safety information in the entry-into-human study (YP39364), have been reviewed.

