**Table 1 Initial Dose of RO7049389 or Placebo**

	Cohort 1	Cohort 2	Cohort 3	Cohort 4 a
SAD	200 mg	400 mg	600 mg	800 mg
MAD	N/A	200 mg q12h b,e	400 mg q12h	600 or 800 mg q24h

- a. Cohort 4 is optional and will be conducted in case that the total daily dose of the estimated efficacious dose from YP39364 is between 400 mg to 600 mg q12h or higher.
- b. The dose of 200 mg q12h in MAD cohort 2 will be optional and will be conducted in case the total daily dose of the estimated efficacious dose from YP39364 is lower than 400 mg q12h.

The rationale for dose selection is described in Section [3.2.1](#).

The highest dose level *and exposure* to be included in this study will be within the dose *and exposure* that has been demonstrated to be safe and well tolerated in FIH Study YP39364.

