### **3.1.2 Dose-Escalation Decision Criteria**

A Safety Review of the data will be conducted by the Principal Investigator, the Medical Monitor, and the Sponsor Clinical Team prior to each RO7049389 dose-escalation.

Escalation to the next dose cohort will be based primarily on the safety and tolerability information (including adverse events [AEs], electrocardiograms [ECGs], vital signs, clinical laboratory test results) up to 48 hours post-dose (SAD), and secondarily on all available PK data up to 24 hours post-dose (SAD) in a minimum of 8 subjects (receiving active study drug or placebo) within the previous cohort. Doses will be escalated by three-fold increments but for higher doses the increments will be smaller than three-fold. The decision to escalate the dose will be made by mutual agreement between the Sponsor and the Investigator.

The MAD phase (Cohorts 2, 3, and 4) can begin after a washout period of at least one week, and once safety and tolerability information through 24 hours post-dose in the SAD phase (see [Figure 1](#)), and available safety and tolerability information from MAD cohorts in the entry-into-human study (YP39364) have been reviewed. Additionally, both the Sponsor and the Investigator must agree that the safety data can support continuing with the multiple-dose phase.

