#### **3.1.2.1 Dose-Escalation Stopping Rules**

Any serious adverse event considered related to study drug will lead to an immediate halt of study drug dosing, dose escalation and enrollment of new subjects until a thorough investigation has been conducted by the Sponsor's Clinical Team and the Principal Investigator. The sponsor or designee will notify all investigators and IRBs/EC, if required (see Section [5.3](#)), regarding the outcome of such investigation. The study will only continue if agreed by the IRBs/EC.

An internal safety review of the unblinded data by Sponsor representatives from Translational Medicine, Drug Safety, Clinical Pharmacology and Biostatistics will be performed prior to each RO7049389 dose-escalation.

Planned dose-escalation will not be implemented if one of the following circumstances occurs in subjects treated with RO7049389, unless it is obvious that the occurrence is not related to the administration of study medication:

- If at any dose level, more than two subjects on active drug experience:
  - Severe and clinically significant (as defined by the Investigator) RO7049389-related AEs of the same character.

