#### **MAD Phase**

RO7049389 or matching-placebo will be administered orally with 240 mL of water to the healthy subjects by investigational staff from Day 1 through to Day 13 q12h, and on Day 14 once in the morning.

*Except for cohort 4, which will be in the fasted state,* a standard breakfast or dinner will be served to healthy volunteers 30 minutes prior to dosing, which should be consumed within 30 minutes. RO7049389 or placebo will then be administered.

Lunch will be served approximately 4-5 hours post-morning-dose. The second daily dose will be administered in the evening, approximately 12 hours after the morning dose.

Timing of meals relative to dosing may be changed according to emerging data.

Guidelines for dietary stipulations are provided in Section 4.4.3 and Section 4.4.4.

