## **6.1 DETERMINATION OF SAMPLE SIZE**

The sample size was determined by practical considerations and not based on statistical power calculations. Approximately four subjects will be enrolled in SAD cohort 1 (2 active treatment and 2 placebo). Approximately twelve subjects will be enrolled in each of the other SAD and MAD cohorts. They will be randomized to either active treatment (10 subjects per dose level) or placebo (2 subjects per dose level).

With ten subjects on active drug per dose group or cohort, there is a 94% chance to observe at least one AE that has an incidence rate of 25% in the population.

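### If Cohort 2 MAD is run, the rule for starting Cohort 3 MAD (400 mg q12h) asks for no data from it; the step to Cohort 4 MAD has the same gap

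*Combined protocol and SAP*

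**What the plan says.** Section 3.1.2 makes the MAD start in Cohorts 2, 3 and 4 depend on four things: a washout of at least a week, SAD safety and tolerability through 24 hours, a check that "available safety and tolerability information from MAD cohorts in the entry-into-human study (YP39364) have been reviewed", and agreement between Sponsor and Investigator that the safety data support continuing. Section 3.1.1 restates the data inputs as "safety information through 24 hours post-dose in the SAD phase at the same cohort" plus available YP39364 safety, and the synopsis is similar. None of the three versions names multiple-dose data from this study, and none names PK.

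Moving to the next cohort also rests on single-dose data. Under Section 3.1.2 it uses safety "up to 48 hours post-dose (SAD), and secondarily on all available PK data up to 24 hours post-dose (SAD"), in at least 8 subjects of the previous cohort. Section 3.1.1 and the synopsis give 24 hours for this step.

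Table 1 sets Cohort 2 MAD at 200 mg q12h, Cohort 3 MAD at 400 mg q12h and optional Cohort 4 MAD at 600 or 800 mg q24h. Its footnote b says "The dose of 200 mg q12h in MAD cohort 2 will be optional", to be run if the estimated efficacious dose is below 400 mg q12h. Footnote a reserves Cohort 4 for an estimate of 400 to 600 mg q12h or higher. The text below the table limits dose and exposure to a level "that has been demonstrated to be safe and well tolerated in FIH Study YP39364".

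**The concern.** The study is run because safety and PK may differ between Chinese and non-Chinese subjects (Section 1.3.1). The first multiple-dose cohort is the first direct evidence on that question for repeated dosing, yet no stated rule makes a higher multiple-dose regimen wait for any of it.

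Single-dose data do not fill the gap. SAD dosing is fasted, while MAD Cohorts 2 and 3 are fed (Section 3.1.1.3). Cohort 3 takes 600 mg once in SAD but 800 mg a day in MAD. A single dose also cannot show effects that build up with repeated dosing.

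At stake is whether ten active subjects begin a higher regimen before the lower one has been observed long enough for the stopping rules in Section 3.1.2.1 to have something to act on.

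**Working it through.** **The plan's own figure.** Section 6.1 says "there is a 94% chance to observe at least one AE that has an incidence rate of 25% in the population". With 10 active subjects, 1 − 0.75^10 = 0.944, so the figure is reproduced. It presupposes that all ten are observed for the whole period to which the 25% refers.

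**Inputs for the timeline**
- Washout w: at least 7 days (Section 3.1.2), taken as equal in both cohorts.
- Earliest gap between SAD doses of successive cohorts: 2 days (48-hour rule, Section 3.1.2), or 1 day (24-hour wording, Section 3.1.1 and synopsis).
- Review interval r: days from the 48-hour cut to the Cohort 3 SAD dose. The plan does not state it, so a range is shown.
- Doses in a q12h course: "from Day 1 through to Day 13 q12h, and on Day 14 once in the morning" (Section 4.3.2.1), so 13 × 2 + 1 = 27.
- One dosing date per cohort is assumed.

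**Timeline.** Put the Cohort 2 SAD dose at day 0.
- Cohort 2 MAD Day 1 falls on day w.
- The Cohort 3 SAD dose falls on day 2 + r, so Cohort 3 MAD Day 1 falls on day 2 + r + w.
- Cohort 2 is then on MAD Day (2 + r + w) − w + 1 = 3 + r. The washout cancels.
- Doses given before that morning: 2 × (2 + r), up to 27.

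| r (days) | Cohort 2 MAD day when Cohort 3 MAD starts | Doses of 200 mg given |
|---|---|---|
| 0 | 3 | 4 of 27 (15%) |
| 5 | 8 | 14 of 27 (52%) |
| 12 | 15 | 27 of 27 |

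Under the 24-hour wording with immediate review, the start falls on Day 2, after 2 of 27 doses. Cohort 2 dosing is complete first only if the SAD doses are at least 14 days apart, which the text does not require.

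**Illustration on the plan's own benchmark.** Assume that the 25% is the incidence of any AE over a 14-day course and that the hazard is constant. The chance that at least one of 10 active subjects has shown the event after d days is 1 − 0.75^(10d/14):
- d = 2: 1 − 0.75^(20/14) = 0.34
- d = 7: 1 − 0.75^5 = 0.76
- d = 14: 1 − 0.75^10 = 0.94

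**Step to Cohort 4.** The same arithmetic puts the earliest start on Cohort 3 MAD Day 3. The amount per dose rises from 400 mg to 600 or 800 mg. The daily dose goes from 800 mg to 600 or 800 mg, so it is equal or lower. Dosing changes from fed to fasted. Section 1.2.2 lists the YP39364 MAD cohorts at the 2 June 2017 cutoff as 200 mg fasted, 200 mg fed and 400 mg fed, all BID. None is once daily, and none exceeds 400 mg per dose.

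**Which step arises.** Read literally and for a fixed efficacious-dose estimate, footnotes a and b select either Cohort 2 MAD (below 400 mg q12h) or Cohort 4 (400 mg q12h and above). One of the two MAD-to-MAD steps then arises on either branch.

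**The case against.** The case against is substantial, and most of it stands as a limit on the size of the point.

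- **Bridging design.** The study leans on YP39364 in order to test fewer doses. YP39364 had given 200 mg fed and 400 mg fed BID for 14 days, reported as well tolerated in a preliminary blinded review. That covers both regimens in the Cohort 2 to 3 step. It does not cover Cohort 4 at the stated cutoff, although later YP39364 data may do so.
- **Cohort 2 MAD is optional.** If it is not run, Cohort 3 is the first MAD cohort here and there is nothing to overlap with.
- **Existing controls.** Section 3.1.2.1 halts dosing for any related SAE. It bars escalation when dose or exposure exceeds what YP39364 evaluated, and it allows other findings to stop escalation whatever their incidence. Section 4.2.1 adds a review of safety and available PK before escalation decisions. Section 3.1.2 requires Sponsor and Investigator agreement and does not restrict which safety data they consider. None of these sets a minimum follow-up of the preceding MAD cohort.
- **A MAD step may already count as a dose-escalation.** The paragraph sits under that section title. This is a fair reading, but the text does not say so, and even on that reading no minimum is set.
- **Figure 1** is cited in the MAD-start rule and is not available here. It may show a sequence.

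A reader might go further and infer that MAD exposure goes unchecked against PK. The exposure bar and the Section 4.2.1 review speak against that. What holds is only that the MAD-start rule itself names no PK.

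A reader might also want the chance that the rule beginning "If at any dose level, more than two subjects on active drug experience" would have fired by Day 3. The documents do not support such a figure. The 25% in Section 6.1 concerns any AE, whereas that rule concerns severe or clinically significant drug-related findings of the same character.

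**Conclusion.** The point holds in a limited form. If Cohort 2 MAD is run, the text requires nothing from it before 400 mg q12h starts, and the earliest start falls on its Day 3 of 14, after 4 of 27 doses. The same gap applies between Cohort 3 MAD and Cohort 4 MAD, where the YP39364 support listed at the cutoff is thinner.

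Day 3 is an earliest case. It rests on the 48-hour rule, immediate review, equal washouts and single-date dosing. Each added day of review moves the start one day later, and from 12 days on there is no overlap. The 34% in the illustration also needs a constant hazard and concerns any AE.

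A reader might infer that the plan intends overlapping MAD cohorts or exposes subjects to an unacceptable risk. The documents do not support that: they permit the overlap without planning it, and the YP39364 data and general controls limit what could go wrong. This is an inexpensive safeguard to consider.

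**What to change.** In Section 3.1.2, and likewise in Section 3.1.1 and the synopsis, add the following.

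- *A MAD regimen with a higher amount per dose or a higher total daily dose than the preceding MAD cohort in this study starts only after review of that cohort's safety and tolerability through about Day 7, if it was run, together with available PK from this study and YP39364.*
- *This step counts as a dose-escalation under Section 3.1.2.1.* Its reviews, stopping rules and exposure bar then apply without argument.

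Defining the step by amount per dose or daily dose brings in Cohort 3 to 4, where only the amount per dose rises. Day 7 is a proposal and can move once time to steady state is known from YP39364. The decision stays with the Sponsor and the Investigator, and no numeric limit is added.

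Cost: with w = 7, data through Cohort 2 MAD Day 7 are complete on day 14, against an earliest Cohort 3 MAD start on day 2 + 7 = 9. The delay is at most 5 days plus review time (6 under the 24-hour wording, 14 − 8). There is none beyond review if the cohorts are already that far apart. Taking the delay before the Cohort 3 SAD dose keeps the washout near one week. The change needs protocol wording and one PK summary, with no extra subjects or samples. If Figure 1 already shows sequential MAD cohorts, only the wording has to catch up.

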#### **3.1.2.1 Dose-Escalation Stopping Rules**

Any serious adverse event considered related to study drug will lead to an immediate halt of study drug dosing, dose escalation and enrollment of new subjects until a thorough investigation has been conducted by the Sponsor's Clinical Team and the Principal Investigator. The sponsor or designee will notify all investigators and IRBs/EC, if required (see Section [5.3](#)), regarding the outcome of such investigation. The study will only continue if agreed by the IRBs/EC.

An internal safety review of the unblinded data by Sponsor representatives from Translational Medicine, Drug Safety, Clinical Pharmacology and Biostatistics will be performed prior to each RO7049389 dose-escalation.

Planned dose-escalation will not be implemented if one of the following circumstances occurs in subjects treated with RO7049389, unless it is obvious that the occurrence is not related to the administration of study medication:

- If at any dose level, more than two subjects on active drug experience:
  - Severe and clinically significant (as defined by the Investigator) RO7049389-related AEs of the same character.

**RO7049389—F. Hoffmann-La Roche Ltd**

31/Protocol YP39406, Version 4

- Clinically significant RO7049389-related laboratory abnormalities of the same character (e.g., ALT or AST $>3\times$ ULN, and total bilirubin $>2\times$ ULN).
- Clinically significant RO7049389-related changes in vital signs or ECGs of the same character (e.g., QTcF $>500$  msec, or  $>60$  msec longer than the pre-dose baseline, within the first 48 hours post-dose).
- It is predicted that further dose-escalation will not result in a further increase in plasma exposure.

- The proposed dose *or exposure* exceeds those previously evaluated in the study YP39364.
- Other findings (regardless of the incidence rates) that at the joint discretion of the Sponsor and the Investigator indicate dose-escalation should be halted.

If dose-escalation is stopped, lower doses within the tolerated dose range could be investigated, or a dose repeated in the subsequent cohorts by mutual agreement between the Sponsor and Investigator, in order to increase the amount of data within this tolerated dose range.

For an individual subject, dosing should not continue if there are:

- Clinically significant RO7049389-related changes in safety parameters that are considered not acceptable by the Investigator and/or the Sponsor; or
- Poor gastrointestinal (GI) tolerability that is considered to affect the subject's wellbeing and/or the PK evaluation.

Due to the exploratory nature of this clinical study, its conduct can be discontinued at any time at the discretion of the Sponsor. This will not constitute a premature termination of the study.

### **3.1.3 End of Study**

The end of the study is defined as the date when the last study subject last observation (LSLO) occurs. LSLO is expected to occur 28 days after the last dose is administered.

## **3.2 RATIONALE FOR STUDY DESIGN**

The rationale for the design of study YP39406 is given in Section [1.3.1](#).

### **3.2.1 Rationale for Dosage Selection**

The first SAD cohort will receive 200 mg (~1/4 of the total projected clinically efficacious dose). This starting-dose is considered to have been safe and well tolerated in the FIH Study YP39364.

RO7049389—F. Hoffmann-La Roche Ltd  
32/Protocol YP39406, Version 4

Furthermore, the starting-dose level of 200 mg is considered to be safe based on FDA guidance. [REDACTED]

[REDACTED] Using the lowest HED of 40 mg/kg [REDACTED] and a safety factor of 10, the maximum recommended starting-dose (MRSD) for a 60 kg individual is 240 mg. The starting-dose of 200 mg proposed in this study is approximately 1.2-fold lower than the MRSD.

Subsequent dose-levels may be adjusted based on the PK, tolerability and safety results from FIH Study YP39364 and available data from current Study YP39406. The highest dose-level *and exposure* to be included in this study will be within the dose range *and exposure* which has been demonstrated to be safe and well tolerated in FIH Study YP39364.

### **3.2.2 Rationale for Study Population**

The study will be conducted in Chinese healthy, male and female subjects of non-childbearing potential, 18 to 60 years of age. The absence of confounding diseases and co-medications in healthy subjects allows for a clearer and more consistent assessment of drug disposition and safety profile.

The data generated from this study will help to evaluate potential ethnic differences between Chinese and non-Chinese subjects with regards to safety, tolerability and pharmacokinetic characteristics that will provide guidance on future clinical studies and optimize the benefit-risk in Chinese HBV patients.

## **3.3 OUTCOME MEASURES**

### **3.3.1 Safety Outcome Measures**

The safety outcome measures for this study are as follows:

- Incidence and severity of adverse events.
- Incidence of laboratory abnormalities, based on hematology, clinical chemistry, coagulation, and urinalysis test results.
- ECGs.
- Vital signs including blood pressure (BP), pulse rate and body temperature.

**RO7049389—F. Hoffmann-La Roche Ltd**  
33/Protocol YP39406, Version 4

### **3.3.2 Pharmacokinetic Outcome Measures**

Plasma concentrations will be measured by specific validated methods. Pharmacokinetic (PK) parameters will be estimated using standard non-compartmental methods for RO7049389.

The pharmacokinetic outcome measures for this study are as follows:

PK parameters (SAD):

- $C_{\max}$ : Maximum observed plasma concentration
- $T_{\max}$ : Time to maximum observed plasma concentration
- $AUC_{0-\text{last}}$ : Area under the plasma concentration versus time curve up to the last measurable concentration
- $AUC_{0-\infty}$ : Area under the plasma concentration versus time curve extrapolated to infinity
- $T_{1/2}$ : Apparent terminal phase half-life
- $CL/F$ : Apparent clearance after oral administration

PK parameters (MAD):

- $C_{\max}$ : Maximum observed plasma concentration after single-dose and at steady-state
- $T_{\max}$ : Time to maximum observed plasma concentration after single-dose and at steady-state
- $C_{\text{trough}}$ : Trough plasma concentration
- $AUC_{0-t}$ : Area under the plasma concentration-time curve for a dosing interval after single-dose and at steady-state
- $T_{1/2}$ : Apparent terminal phase half-life after single-dose and at steady-state
- Accumulation index of RO7049389

PK parameters (SAD and MAD):

- Plasma samples collected in the study will be qualitatively and/or quantitatively analyzed for the metabolites (M5, M6, and M11) of RO7049389 in selected samples.

## **4. MATERIALS AND METHODS**

### **4.1 STUDY POPULATION**

Due to the nature of this study, the actual number of subjects will be determined during the study. This study may require up to 76 subjects, including:

- About 40 healthy subjects to be enrolled in Cohort 1 of 4 subjects and Cohort 2 to Cohort 4 of about 12 subjects each.

**RO7049389—F. Hoffmann-La Roche Ltd**

34/Protocol YP39406, Version 4

- Up to 36 healthy subjects to be enrolled if new subjects are needed for the MAD phase, in case of non-safety related discontinuations between two periods (i.e., replacement subjects),
- For each part, up to two back-up subjects can undergo the preparatory activities in order to replace participants who withdraw from the study for non-safety reasons.

Subjects who drop out of the study for non-safety reasons may be replaced to ensure sufficient data to characterize the safety and PK profile, and to make a dose-escalation decision. Subjects who withdraw from the study due to poor tolerability, or, due to study drug-related adverse events, will not be replaced.

#### **4.1.1 Recruitment Procedures**

Study subjects will be identified for potential recruitment using pre-screening enrollment logs, IEC/IRB approved newspaper/radio advertisements and mailing lists prior to consenting to take place on this study.

#### **4.1.2 Inclusion Criteria**

Study subjects must meet the following criteria for study entry:

1. Chinese healthy male and female subjects, 18 to 60 years of age, inclusive. Healthy status is defined by absence of evidence of any active or chronic disease following a detailed medical and surgical history, a complete physical examination including vital signs, 12-lead ECG, hematology, blood chemistry, serology and urinalysis.
2. A Body Mass Index (BMI) of between 19 to 27 kg/m^2 inclusive, and a body weight of at least 45 kg.
3. Women should be of non-childbearing potential. Female subjects must be either surgically sterile (by means of hysterectomy and/or bilateral oophorectomy) or post-menopausal for at least one year (defined as amenorrhea $\geq$ 12 consecutive months without another cause, and confirmed by follicle stimulating hormone level $>35$  mIU/mL).
4. For men: agreement to remain abstinent (refrain from heterosexual intercourse) or use contraceptive measures, and agreement to refrain from donating sperm, as defined below:
  - a) With female partners of childbearing potential, men must remain abstinent or use two methods of contraception with their partner, one of which must be a barrier method (i.e., condom), for the duration of the study and for at least 28 days after the last dose of study drug to avoid exposing the embryo. Men must refrain from donating sperm during this same period.
  - b) The reliability of sexual abstinence should be evaluated in relation to the duration of the clinical trial and the preferred and usual lifestyle of the patient. Periodic abstinence (e.g., calendar, ovulation, symptothermal, or post-ovulation methods) and withdrawal are not acceptable methods of contraception.
  - c) Other acceptable forms of contraception for this study include vasectomy, bilateral tubal occlusion, intrauterine device (IUD) or proper use of hormonal contraceptives.

